**Protocol Amendment Summary of Changes Table**

Document History		
Document	Version Date	Summary of Changes and Rationale
Original Protocol	14 November 2018	Not applicable (N/A)

## **1. PROTOCOL SUMMARY**

### **1.1. Synopsis**

Not applicable.

### **1.2. Schema**

Not applicable.

### 1.3. Schedule of Activities (SoA)

The **SoA** table provides an overview of the protocol visits and procedures. Refer to the **STUDY ASSESSMENTS AND PROCEDURES** section of the protocol for detailed information on each procedure and assessment required for compliance with the protocol.

The investigator may schedule visits (unplanned visits) in addition to those listed in the **SoA** table, in order to conduct evaluations or assessments required to protect the well-being of the participant.

Visit Identifier a	Screening b	Study Period																Follow Up s or Early Termination t		
		Days Relative to Day 1	Day -28 to Day -2	Day -1	Day 1						Day 2	Day 3	Day 4	Day 5	Day 6	Day 7	Day 8		Day 9	Day 10
Hours After Dose			0	2	4	6	8	12	24	48	72	96	120	144	168	192	216	264		
Informed consent	X																			
CRU confinement c		X	→	→	→	→	→	→	→	→	→	→	→	X						
Review inclusion/exclusion criteria	X	X																		
Demography d	X																			
Medical/medication history (update) c	X	X																		
Physical examination, height, and body weight f	X	X												X						X t
Safety laboratory tests g	X	X							X					X						X t
Contraception check h		X												X						X s,t
Alcohol/tobacco use & Breath alcohol test i	X	X																		
FSH (only females amenorrheic for at least 12 months)	X																			
Urine drug testing	X	X																		
Supine 12-Lead ECG j	X		X		X									X						X t
Blood pressure and pulse rate k	X		X						X					X						X t
Child-Pugh assessment l	X																			

Visit Identifier a	Screening b	Study Period																Follow Up s or Early Termination t	
		Days Relative to Day 1	Day -1	Day 1						Day 2	Day 3	Day 4	Day 5	Day 6	Day 7	Day 8	Day 9		Day 10
Hours After Dose	Day -28 to Day -2		0	2	4	6	8	12	24	48	72	96	120	144	168	192	216	264	
Hepatitis B (HepBsAg, HepBcAb), Hepatitis C (HCVAb), and HIV tests	X																		
Study treatment administration m		X																	
PK blood sampling n			X	X	X	X	X	X	X	X	X	X	X	X	X	X	X	X	
Protein binding blood sampling o			X			X	X												
Pharmacogenomics blood sampling (CYP2D6) p		X																	
Pfizer Prep D1 banked sample(s) q		X																	
Prior/concomitant treatments	X	X	→	→	→	→	→	→	→	→	→	→	→	→	→	→	→	→	X s,t
CRU discharge f														X					
Serious and nonserious adverse event monitoring	X	X	→	→	→	→	→	→	→	→	→	→	→	→	→	→	→	→	X s,t

Abbreviations: → = ongoing/continuous event; AE = adverse event; BMI = body mass index; CRU = clinical research unit; CYP = cytochrome P450; ECG = electrocardiogram; FSH = follicle-stimulating hormone; HCVAb = hepatitis C antibody; HepBcAb = hepatitis B core antibody; HepBsAg = hepatitis B surface antigen; HIV = human immunodeficiency virus; PK = pharmacokinetic.

- Day relative to start of study treatment (Day 1).
- Screening will be performed within 28 days prior to the dosing of investigational product (dacomitinib) (Section 4.1).
- All participants will be admitted to the CRU on Day -1. All participants will be required to stay in-house at least until the collection of the 144 hour PK sample following dacomitinib dosing.
- Demographics will include participant height, weight, race, age and gender data collected during Screening.
- Medical/medication history will include a history of illegal drug, alcohol, and tobacco use, as well as blood donation within 60 days prior to first dose. Medical/medication history will be recorded at Screening and updated when the participant is admitted to the CRU on Day -1.
- A complete physical examination may be conducted by a physician, trained physician's assistant, or nurse practitioner as acceptable according to local regulation at the investigator site either during Screening or Day -1 only (height and body weight must be obtained at Screening to obtain BMI for eligibility criteria). If complete physical examination is performed during the screening visit, then only a brief physical examination is needed on Day -1. A brief physical examination may be conducted at the discretion of the investigator on Day 7 prior to discharge for new or ongoing AEs and during early termination.

- g. Safety laboratory assessments including urinalysis, hematology (including prothrombin time/partial thromboplastin time), and chemistry will be performed at Screening, on Day -1, on Day 2, Day 7 prior to discharge and during early termination. All assessments must be collected following at least a 4-hour fast. For participants with severe hepatic impairment (Cohort 1), the Day -1 safety labs including liver function assessments and evaluation of renal function must be completed prior to dacomitinib dosing on Day 1, for review of inclusion/exclusion criteria. Additional assessments may be performed at the discretion of the investigator.
- h. On Day -1, on Day 7 (or any subsequent day that coincides with discharge) and during follow-up or early termination, the investigator or his/her designee will discuss with the participant the need to use highly effective contraception consistently and correctly according to protocol contraception guidelines in [Section 5.3.4](#).
- i. Alcohol/tobacco use and alcohol breath test will be performed during Screening or on Day -1. These tests may also be performed at any other time at the discretion of the investigator.
- j. A single 12-lead ECG will be obtained at Screening, 6 hours post-dose on Day 1, prior to discharge on Day 7 and during early termination. A triplicate ECG will be obtained approximately 2 to 4 minutes apart at pre-dose on Day 1. All ECG assessments will be made following at least a 10-minute rest in a supine position and should be collected before PK sample collection, if scheduled at the same time point.
- k. Supine blood pressure will be determined following approximately 5-minute rest in a supine position.
- l. The modified Child-Pugh assessment as outlined in [Appendix 8](#) should be followed.
- m. On Day 1, administration of dacomitinib will occur with approximately 8 oz (240 mL) of ambient temperature water after at least a 10 hour fast. Following dacomitinib administration, no food will be allowed for at least another 4 hours post dose except that a light snack or juice may be provided to a diabetic participant.
- n. Blood samples (3 mL each) for PK will be taken upon completion of ECGs, blood pressure and pulse measurements. Serial blood samples for the measurements of dacomitinib and its metabolite, PF-05199265, will be collected prior to dosing and at 2, 4, 6, 8, 12, 24, 48, 72, 96, 120, 144, 168, 192, 216 and 264 hours following dosing.
- o. Blood samples (10 mL each) will be collected prior to dacomitinib dosing and at 6 and 8 hours following dosing.
- p. One (1) blood sample (3 mL) only will be collected on Day -1 for CYP2D6 genotyping.
- q. One (1) 4 mL blood sample should be drawn on Day -1. If not collected on the designated collection day, collect at the next available time point when biospecimens are being collected in conjunction with a participant visit.
- r. Participants will be eligible for discharge from the CRU following completion of the following: 144-hour PK sample collection, a single supine 12-lead ECG, supine blood pressure and pulse rate, discussion of the need for highly effective contraception, safety laboratory test, evaluation of participant-reported adverse events, review of prior and concomitant medications, brief physical examination, and body weight. Day 7 safety laboratory tests can be collected early (ie. On Day 6) so results are available in time for intended participant discharge on that day.
- s. All participants will be followed up by phone call at least 28 days and up to 35 days after the administration of the dacomitinib dose for potential AEs, concomitant treatment use and to confirm appropriate contraception usage.
- t. Participant withdrawal/early termination activities will include a brief physical examination (if there is a new or ongoing AE or a previous clinically significant abnormal physical finding), safety laboratory tests, a contraception check, a single supine 12-lead ECG, supine blood pressure and pulse rate, concomitant treatment and AE assessment.

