#### 2.2.4. Clinical Overview

As of 29 July 2016, 3182 patients have been treated in 17 clinical studies and 143 healthy participants and 15 patients with solid tumors have been treated in 9 clinical pharmacology studies. Dacomitinib was administered to 2148 of the patients in these trials, in 1975 patients as a single agent or in combination with figitumumab (CP-751,871, a monoclonal antibody targeting the IGF1R), crizotinib (an anaplastic lymphoma kinase [ALK], mesenchymal-epithelial transition [MET] and c-ROS oncogene 1 [ROS1] tyrosine kinase inhibitor), or gedatolisib (PF-05212384, a phosphoinositide 3-kinase [PI3K]/mTOR inhibitor), and in 173 patients in Phase 1 combination therapy studies. Most patients treated in clinical studies had locally advanced or metastatic NSCLC. There were 1473 patients with NSCLC who received single-agent dacomitinib 45 mg once daily (QD), the maximum tolerated dose as determined by Studies A7471001, A7471003, and A7471005. Of these patients, 394 patients had NSCLC with EGFR-activating mutations; 255 of these patients received dacomitinib as first-line treatment.

The most frequently reported adverse events (AEs) in  $\geq 10\%$  of patients included GI-related, skin-and-nail-related, respiratory, and constitutional events.

Results from Study A7471015 indicated that dacomitinib can be administered with or without food. Following a single oral administration of dacomitinib at 45 mg in patients with advanced malignant solid tumors, the median time to reach the maximum observed plasma concentration ( $T_{max}$ ) of dacomitinib occurred approximately at 5 to 6 hours after dosing. Dacomitinib underwent extensive extravascular distribution with a geometric mean apparent volume of distribution ( $V_z/F$ ) ranging from 2424 to 2537 L/h and had a mean apparent terminal plasma half-life ( $t_{1/2}$ ) ranging from 54 to 80 hours. Following administration of multiple daily doses of dacomitinib at 45 mg to patients with advanced malignant solid tumors, steady-state was reached within 14 days, accumulation of dacomitinib in patients ranged from 5.0 to 6.4-fold for AUC, reflecting the observed long  $t_{1/2}$ . The geometric AUC over dosing interval ( $AUC_{tau}$ ) and  $C_{max}$  of dacomitinib at steady-state ranged from 1621 to 2213 ng•h/mL and 79.5 to 108.0 ng/mL, respectively. Plasma exposure of dacomitinib increased proportionally with dose in the dose range of 2 mg to 60 mg, indicating linear PK.

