#### **4.2. Scientific Rationale for Study Design**

A parallel group design will be utilized to compare the dacomitinib PK between participants with normal hepatic function and participants with severely impaired hepatic function but are otherwise healthy. The participants from the severely impaired hepatic function cohort will be recruited first, then the participants from the normal hepatic function cohort will be recruited later to match the median demographics from severe hepatic impairment group. The modified Child-Pugh classification system will be the method used in this study to identify participants with severe hepatic impairment. Additionally, total bilirubin and AST will be assessed in this study as per the recommendations of the National Cancer Institute Organ Dysfunction Working Group Criteria for assessment of hepatic impairment.

This study is designed using a single dose of dacomitinib considering that single dose plasma PK of dacomitinib has been documented to be generally predictive of exposure at steady state. All participants enrolled in this study will receive 1 single oral 30 mg dose of dacomitinib administered as tablet(s). The PK samples will be collected serially up to 264 hours postdose, which has been shown to be adequate for participants with normal, mild or moderate hepatic function. This sampling duration is also expected to be adequate for characterizing the elimination phase of the plasma dacomitinib concentration-time profile for participants with severe hepatic impairment, for whom the elimination half-life of dacomitinib may be prolonged.

Dacomitinib undergoes both oxidative metabolism and glutathione conjugation. Oxidative metabolism of dacomitinib involves CYP2D6 for the formation of major circulating metabolite, PF-05199265, which has similar in vitro pharmacological activities as dacomitinib. Therefore the plasma PK for both dacomitinib and PF-05199265 will be evaluated in this study.

Since CYP2D6 metabolism is a component of dacomitinib elimination, genetic polymorphisms of CYP2D6 may have the potential to alter dacomitinib PK. A 3-mL blood sample will be collected on Day -1 from each participant for genotyping CYP2D6 polymorphism. Only participants identified as an CYP2D6 extensive metabolizer (EM) or CYP2D6 intermediate metabolizer (IM) will be included in the primary statistical analysis to evaluate the impact of severe hepatic impairment on dacomitinib plasma PK.

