### **7.2. Participant Discontinuation/Withdrawal From the Study**

A participant may withdraw from the study at any time at his/her own request, or may be withdrawn at any time at the discretion of the investigator for safety, behavioral, compliance, or administrative reasons.

At the time of discontinuing from the study, if possible, an early discontinuation visit should be conducted. See the [SoA](#) for assessments to be collected at the time of study discontinuation and follow-up and for any further evaluations that need to be completed.

The early discontinuation visit applies only to participants who are randomized and then are prematurely withdrawn from the study. Participants should be questioned regarding their reason for withdrawal. The participant will be permanently discontinued from the study at that time.

If a participant withdraws from the study, he/she may request destruction of any remaining samples, but data already generated from the samples will continue to be available, and may be used to protect the integrity of existing analyses. The investigator must document any such requests in the site study records.

If the participant withdraws from the study and also withdraws consent (see below) for disclosure of future information, no further evaluations should be performed and no additional data should be collected. The Sponsor may retain and continue to use any data collected before such withdrawal of consent.

When a participant withdraws from the study because of an SAE, the SAE must be recorded on the CRF and reported on the Clinical Trial (CT) SAE Report.

Lack of completion of all or any of the withdrawal/early termination procedures will not be viewed as protocol deviations so long as the participant's safety was preserved.

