### 7.3. Pharmacokinetic Parameters

Actual PK sampling times will be used in the derivation of PK parameters.

If a PK parameter cannot be derived from a subject's concentration data, the parameter will be coded as NC (ie, not calculated). (Note that NC values will not be generated beyond the day that a subject discontinues).

In summary tables, statistics will be calculated by setting NC values to missing; and statistics will be presented for a particular hepatic function group with  $\geq 3$  evaluable measurements. For statistical analyses (ie, analysis of variance), PK parameters coded as NC will also be set to missing; and analyses will not be performed for a particular parameter if more than 50% of the data are NC.

If an individual subject has a known biased estimate of a PK parameter (due for example to an unexpected event such as vomiting before all the compound is adequately absorbed in the body), this will be footnoted in summary tables and will not be included in the calculation of summary statistics or statistical analyses.

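### The early termination visit draws safety blood but no PK sample, so some early leavers lose one available late concentration

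*Protocol*

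**What the plan says.** Footnote t of the SoA (Protocol 1.3) sets out the early termination visit: a brief physical examination where indicated, then "safety laboratory tests, a contraception check, a single supine 12-lead ECG, supine blood pressure and pulse rate, concomitant treatment and AE assessment". No PK sample is on the list, and the PK row of the table is blank in the Follow Up/Early Termination column. Protocol 7.2 adds nothing of its own: "See the [SoA](#) for assessments to be collected at the time of study discontinuation".

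Scheduled PK samples are taken "prior to dosing and at 2, 4, 6, 8, 12, 24, 48, 72, 96, 120, 144, 168, 192, 216 and 264 hours following dosing" (SoA footnote n). On confinement, the SoA footnotes say: "All participants will be required to stay in-house at least until the collection of the 144 hour PK sample following dacomitinib dosing". The 168, 192, 216 and 264 h samples therefore fall after the earliest discharge.

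The primary endpoints are Cmax and AUCinf, with AUClast replacing AUCinf if AUCinf cannot be reliably estimated (Protocol 3). SAP 7.3 states: "Actual PK sampling times will be used in the derivation of PK parameters". The plan aims for 6 PK-evaluable participants per cohort (Protocol 4.1 and 9.2).

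**The concern.** In a single-dose PK study, leaving the study does not stop elimination of the drug. A concentration taken at exit is as informative about the terminal phase as a scheduled one at the same time, and the SAP's use of actual times means it could enter the noncompartmental analysis without any change of method. Blood is being drawn at that visit anyway.

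Late points matter most in the severe cohort, "for whom the elimination half-life of dacomitinib may be prolonged" (Protocol 4.2). With so few participants per cohort, each AUCinf carries weight. If AUCinf is judged unreliable, AUClast takes its place, and AUClast reads low for anyone whose sampling stopped early.

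**Working it through.** **Checks against the plan's own figures.** Table 1 gives 8 participants in Cohort 1 and at most 10 in Cohort 2; 8 + 10 = 18, the stated enrolment. Protocol 8.4 gives at least 17 days for 5 half-lives; 5 × 80 h / 24 = 16.7 days, which agrees with the upper documented half-life.

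**Inputs.** Half-life "ranging from 54 to 80 hours" and Tmax "approximately at 5 to 6 hours after dosing" (both Protocol 2.2.4, patients given 45 mg; 6 h is used for Tmax). No half-life is given for severe impairment; 120 h is assumed as an illustration. The one-compartment shape is also an assumption.

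**Formula.** Concentration is proportional to e^(−kt) − e^(−ka·t), with k = ln 2 / half-life and ka solved from ln(ka/k)/(ka − k) = 6 h. For a late last sample at time t, the share of AUCinf that is extrapolated is e^(−kt) × ka/(ka − k).

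Example at half-life 80 h: k = 0.00866 and ka = 0.753 per hour, so ka/(ka − k) = 1.012.
- Last sample 144 h: e^(−1.248) × 1.012 = 0.287 × 1.012 = 0.291.
- Last sample 240 h: e^(−2.079) × 1.012 = 0.125 × 1.012 = 0.126.

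The table applies linear-up/log-down noncompartmental analysis to the protocol's sampling times, with the terminal slope fitted to points from 24 h on. It agrees with the formula to about 0.1 percentage point. Each cell is the extrapolated share of AUCinf without → with an exit sample.

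| Last scheduled sample, exit time | Half-life 54 h | 80 h | 120 h (assumed) |
|---|---|---|---|
| 72 h, exit 84 h | 40.6% → 34.8% | 54.3% → 49.0% | 66.5% → 62.1% |
| 144 h, exit 156 h | 16.1% → 13.8% | 29.1% → 26.2% | 43.9% → 41.0% |
| 192 h, exit 204 h | 8.7% → 7.5% | 19.2% → 17.3% | 33.3% → 31.0% |
| 216 h, exit 240 h | 6.4% → 4.7% | 15.6% → 12.7% | 29.0% → 25.2% |
| 144 h, three visits missed, exit 240 h | 16.1% → 4.7% | 29.1% → 12.7% | 43.9% → 25.2% |

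In the first four rows the gain runs from 1.2 points (8.7 − 7.5) to 5.8 points (40.6 − 34.8). In the last row it is 11.4, 16.4 and 18.7 points.

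**AUClast.** At half-life 80 h, AUClast covers 70.7% of AUCinf if sampling ends at 144 h, 87.1% if a 240 h exit sample is added, and 89.5% with the full schedule. Relative to a completer, the early leaver reads 1 − 70.7/89.5 = 21% low without the exit sample and 1 − 87.1/89.5 = 3% low with it.

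**Is AUCinf still estimable?** After an exit beyond 144 h, at least six points from 24 h on remain (24, 48, 72, 96, 120 and 144 h). With an assumed 10% assay noise and half-life 80 h, simulation gives an SD of the AUCinf error of 3.1% with last sample 264 h, 3.3% at 216 h, 6.0% at 144 h and 14.3% at 96 h. Losing only the 264 h point costs little.

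**Blood volume.** PK 16 × 3 = 48 mL, protein binding 3 × 10 = 30 mL, genotyping 3 mL and banked sample 4 mL make 85 mL of the stated total of about 140 mL. One more 3 mL tube gives about 143 mL, against the 550 mL limit in Protocol 8.

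**The case against.** A reader might infer that anyone who leaves before 264 h loses a usable AUCinf. The documents do not support that. SAP 7.3 codes a parameter as not calculated only if it cannot be derived, and SAP 8.1 lists the extrapolated percentage, r² and number of points without acceptance limits. The precision figures above also show that a usable estimate normally survives an exit after 144 h.

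A reader might also take the three-missed-visits row as the usual case. Nothing in the documents describes a dropout pattern. Scheduled samples from 24 h on fall at about the dosing clock time on Days 2 to 10 and Day 12, so a termination visit at that hour usually coincides with a sample already due; only Day 11 (240 h) has none. The small gains in the first four rows are the safer guide, and the scheduled samples not taken, rather than footnote t, are the main cause of any loss.

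Other buffers are real. Late exit does not affect Cmax. One primary parameter keeps a participant in the PK parameter set. Enrolment exceeds the 6 needed per cohort, and replacement is possible with sponsor agreement. The termination visit itself is held only if possible, and withdrawal of consent rules out sampling.

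It can also be said that Protocol 7.3 asks sites to reschedule missed visits and that 8.5.1 lets sampling times change. That text serves participants who continue; it does not place a PK draw in the termination visit. So the omission stands, with a limited consequence.

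**Conclusion.** The gap is confirmed: safety blood is drawn at early termination and no PK sample is taken with it. The consequence is one lost late concentration for a participant who exits between scheduled samples or after missing post-discharge visits. That means more extrapolation in AUCinf and more truncation in AUClast, not the automatic loss of the primary endpoint.

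The size is about 1 to 6 percentage points of extrapolation when the preceding scheduled sample was taken, and more if several visits were missed. These figures rest on the one-compartment shape, Tmax of 6 h and the assumed 120 h half-life; a multi-phase decline would change them. The number of early leavers is unknown. This is a minor point, worth making because the remedy costs so little.

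**What to change.** Add to SoA footnote t, with a matching mark in the PK row: *if the early termination visit takes place up to and including 264 h after dosing and the participant still consents to sampling, collect one 3 mL PK sample with the safety laboratory draw, unless a scheduled PK sample has just been taken, and record the actual time.*

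In the SAP, state that this sample is used at its actual time in the noncompartmental analysis and left out of nominal-time concentration summaries and mean or median plots.

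The cost is one extra 3 mL tube and one assay per early leaver. No extra venipuncture is needed. The sample cannot help participants who do not attend or who withdraw consent.
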